3.2 Rationale and risk/benefit assessment

3.2.1 Rationale for study design, doses and control groups

A first administration to man, Phase I, randomised, double blind, placebo controlled, two-part AstraZeneca Global SAD/MAD Study to assess the safety and tolerability and PK of single and multiple oral doses of AZD9668 in healthy volunteers is ongoing. Up to [REDACTED], AZD9668 has been administered in single ascending doses of 2 mg, 10 mg, 30 mg, 60 mg, 120 mg and 150 mg with 36 subjects receiving the active drug and 12 subjects receiving the placebo. No serious adverse events (SAEs) occurred. There were 46 non-serious adverse events (AEs) reported by 24 subjects. The severity for the majority of the events was mild (37/46 AEs); few were reported as moderate (7/46 AEs), and for one subject, two events were reported as severe (syncope associated with a symptomatic

bradycardia, 4 hours 37 minutes after a 2 mg dose). These last two events resolved with supportive care within 3 minutes. The most frequently reported AE was headache (18/10 subjects), followed by musculo-skeletal pain/myalgia/backpain (5/4 subjects) and light headedness (3/2 subjects). None of the AEs were considered by the Investigator to be causally related to the investigational drug. The multiple ascending dose part of this study has commenced on the [REDACTED], at 30 mg daily for 8 days, with no safety or tolerability issues identified so far.

The present study will be conducted in healthy volunteers, in a double blind, placebo controlled manner, and volunteers will be randomised to receive either AZD9668 or placebo

Healthy volunteers will be used in this study in order to optimise compliance with study procedures and to avoid interference with the results from disease processes and other drugs. The inclusion/exclusion criteria are defined such that the volunteers selected will be known to be free of any significant illness when included in the study. This study is being performed double blind in order to minimise both potential selection bias in the allocation of volunteers to specific treatments and bias to the volunteer's data as a result of the volunteer or study personnel being aware of whether a volunteer is receiving AZD9668 or placebo. The placebo control will provide a reference to aid interpretation of safety and tolerability data.

Healthy, male or female (non-childbearing potential), Japanese or Caucasian volunteers will be included; safety, tolerability and PK data will be compared between these populations to enable inclusion of Japanese volunteers in the subsequent clinical development programme for AZD9668. To be considered as 'Japanese', both of the volunteer's parents and both sets of grandparents must be Japanese, the volunteer must have been born in Japan, have a valid Japanese passport, and must not have lived outside Japan for more than 8 years. These criteria ensure representative study population by excluding mixed race or naturalised Japanese living in the West.

The starting dose for cohort 1 will be 30 mg. This dose has been selected as a low dose that was found to be safe and well tolerated based upon the emerging draft data from the AstraZeneca Global SAD/MAD Study. It is proposed that the subsequent single doses will be 60 mg, 120 mg and 150 mg. These are proposed doses only and may change with emerging data from this study. The top dose will be no higher than 150 mg as this is the maximum dose that was administered to healthy volunteers in the AstraZeneca Global SAD/MAD Study and was found to be safe. In addition, modelled PK data from the current study will ensure that the predicted geometric mean C_{max} and $AUC_{(0-24)}$ at the top dose will not exceed 2.5 μ M or 18 μ M.h, respectively. These exposure limits have been determined by the AstraZeneca Human Exposure Limits Committee (HELCC) following a review of the data obtained in the 1-month toxicology studies in the rat and dog. The limits have been set based upon the exposures at the no observed adverse effect level (NOAEL) in rat (370 mg/kg), corrected for the differences in plasma protein binding between the species. The NOAEL in the rat has been used because the free exposures at this dose are lower than those obtained in the dog at the NOEL dose.

The multiple doses for both cohorts 1 and 2 will be selected following a safety review meetings using emerging data from the current study and the AstraZeneca Global SAD/MAD Study. The maximum multiple dose will be capped at a total daily dose of 140 mg. In addition, the emerging PK data from the current study will be modelled to ensure that for the highest dose given, the predicted geometric mean exposures (both $AUC_{(0-24),ss}$ and $C_{max,ss}$) will not exceed 2.5 μM or 18 $\mu\text{M}\cdot\text{h}$, respectively.

Once a day dosing will be used for the single doses to enable investigation of single dose pharmacokinetics, and the twice daily (bid) dosing regimen will be used for the multiple doses because this is the dosing regimen that is planned to be used in patient intervention studies with AZD9668. If bid dosing is not tolerated then once a day dosing will be considered.

3.2.2 Risk/benefit and ethical assessment

The volunteers will have no individual benefit from participation in the study. The early development studies are to enable further investigations to evaluate AZD9668 as a treatment of COPD.

The current knowledge of the possible adverse effects of AZD9668 is based on the pre-clinical safety assessments. The main findings from these, which could be of relevance in human studies, include haematological changes at high doses (90 mg/kg) in a preliminary 28-day toxicity study in dogs; a slight QT prolongation (9%) at a high dose in a dog telemetry study; and slightly elevated plasma creatinine at high doses in repeat-dose studies in dogs and in rat renal function in a single dose study. In the current healthy volunteer study, host defence issues are not expected to be a problem.

For an overall risk benefit assessment of developing a NE inhibitor in COPD, see the Investigator's Brochure

3.3 Selection of study population

3.3.1 Study selection record

The Investigator must keep a record of volunteers who were considered for enrolment but never enrolled eg, volunteer screening log, according to local procedures. This information is necessary to establish that the subject population was selected without bias.

Replacements will be considered for all cases of volunteer drop-out, except for reasons of AE. This will all be at the Investigator's discretion

3.3.2 Inclusion criteria

For inclusion in the study volunteers must fulfil all of the following criteria:

1. Provision of signed, written informed consent.
2. Healthy Japanese or Caucasian volunteers. To be considered as 'Japanese', both of the volunteer's parents, and both sets of grandparents must be Japanese. The

volunteer must have been born in Japan, have a valid Japanese passport and must not have lived outside Japan for more than 8 years.

3. Male or female aged between 20-45 years (inclusive).
4. Weight 45-90 kg and Body Mass Index (BMI=weight/height²) 18-30 kg/m² as measured at Visit 1b.
5. Females must be post menopausal (defined as amenorrhoeic for 12 months and follicle-stimulating hormone (FSH) plasma concentration within the postmenopausal range as defined by the laboratory) or surgically sterile (defined as having undergone bilateral oophorectomy and/or hysterectomy; tubal ligation on its own is not adequate).
6. Have normal physical examination, laboratory values and vital signs (blood pressure and pulse) as measured at Visit 1b, unless the Investigator considers an abnormality to be clinically irrelevant.
7. Have a normal resting ECG at Visit 1b, as judged by the Investigator, with normal QTc interval (<450 ms for both males and females), unless the Investigator considers an abnormality to be clinically irrelevant.
8. Have negative screens for Hepatitis B surface antigen, Hepatitis C antibodies and human immunodeficiency virus (HIV) 1 and 2 antibodies.

For inclusion in the genetic component of the study, volunteers must fulfil the following criterion:

1. Provision of signed, separate written informed consent for genetic research.

If a volunteer declines to participate in the genetic component of the study, there will be no penalty or loss of benefit to the volunteer. The volunteer will not be excluded from other aspects of the study described in this clinical study protocol, so long as they consent.

3.3.3 Exclusion criteria

Any of the following is regarded as a criterion for exclusion from the study:

1. Habitual smokers (the volunteer may be an occasional smoker providing that he/she is able to avoid smoking during the periods in the [REDACTED] Volunteers who smoke >10 cigarettes a day will be excluded from the study.
2. Symptoms of any clinically significant illness within two weeks prior to Visit 2.
3. Use of any prescribed medication (other than hormone replacement therapy [HRT]) or use of any non-prescribed preparations (other than paracetamol 1 g up to a

maximum daily dose of 4 g, permitted for occasional use) within two weeks prior to Visit 2.

4. Use of any herbal preparations and/or vitamins in the 7 days prior to Visit 1b, at the Investigator's discretion.
5. A history, or presence, of conditions known to interfere with the absorption, distribution, metabolism or excretion of drugs, eg, haematological, gastrointestinal, hepatic or renal disease, etc.
6. A definite, or suspected, personal history of intolerance or hypersensitivity to drugs and/or their excipients, judged to be clinically relevant by the Investigator.
7. Surgery or significant trauma within 90 days of Visit 2.
8. Involvement in the planning and conduct of the study (applies to both AstraZeneca and CRO staff).
9. Participation in a clinical study involving administration of another investigational medicinal product, or a new formulation of a marketed drug, the last follow-up visit of which is within 90 days prior to Visit 2 in this study (Note: participation is defined as having received at least one dose of investigational product).

or,

Participation in a method development study, where no drugs were given, but invasive procedures were used, the last follow-up visit of which is within 30 days prior to Visit 2 in this study.

10. If participation in the study would result in the donation of more than 1200 mL of blood in the year prior to the planned final study visit, or donation of blood in total >500 mL within the 90 days before the end of the study.
11. A significant history of alcohol abuse or consumption of greater than 28 units/week in males or 21 units/week in females (1 unit is equivalent to half a pint [285 mL] of beer, 1 glass of wine [125 mL] or 1 measure of spirits [25 mL]).
12. A significant history of drug abuse (including benzodiazepines) or positive drugs of abuse test at Visit 1b.
13. Anticipated difficulty with venous access.
14. Volunteers who, in the opinion of the Investigator, should not participate in the study.
15. Planned in-patient surgery, dental procedure or hospitalisation during the study.

If a volunteer fails the inclusion/exclusion criteria, the assessment may be repeated once only at discretion of the Principal Investigator.

3.3.4 Restrictions

Volunteers will be required to adhere to the dietary and activity restrictions as outlined below:

Dietary restrictions

1. To avoid false positive drugs of abuse test, volunteers should abstain from consuming poppy seeds (as found on speciality breads) from Visit 1a until the last assessment at Visit 5.
2. Volunteers should abstain from the consumption of energy drinks containing glucuronolactone or taurine (eg, Red Bull) from Visit 1a until the last assessment at Visit 5.
3. Volunteers should abstain from drinking alcohol from 48 hours prior to Visit 1b and until the last assessment at each visit.
4. Volunteers should refrain from consuming grapefruit, grapefruit juice or other grapefruit containing products from 7 days prior to Visit 2 until the last assessment at Visit 5.
5. Volunteers should restrict the consumption of caffeine-containing drinks (eg, coffee, tea, cocoa, chocolate, cola, and “sports” drinks containing caffeine) to 4 cups per day, and caffeine-containing foods should be restricted from 72 hours prior to Visit 2 until the last assessment at Visit 5.
6. On waking on the morning of each dosing day volunteers will consume 150 mL of water. This must be a minimum of 1 hour before dosing. No further liquids will be allowed before dosing and for 2 hours after dosing. During the multiple dosing, volunteers will also not be allowed fluids for 2 hours before and 2 hours after their evening dose.
7. For the single doses, volunteers will be required to fast from midnight the night before dosing day (except water for thirst) prior to safety samples being taken. No food is allowed until 4 hours after dosing.

For the multiple dosing, volunteers will be required to fast from midnight the night before dosing (except water for thirst). On Days 13 and 19, no food is allowed until 4 hours after the morning dose and for 2 hours before and 2 hours after their evening dose. On Days 14-18, volunteers will have the same restrictions except that they will be allowed a light breakfast at 2 hours post the morning dose.

Activity restrictions

The following activity restrictions are required during both the single and multiple dose phases of the study:

1. Volunteers should refrain from strenuous physical activity, which is not in the volunteer's normal daily routine, from 72 hours prior to Visit 2 until discharge from the study.
2. Volunteers should abstain from taking any prescribed medication (apart from HRT) from two weeks prior to Visit 2 until completion of Visit 5. However, this should not obviate necessary medical treatment.
3. Volunteers should abstain from taking non-prescribed medication (including over-the-counter [OTC] drugs, drugs bought over the internet, herbal remedies and vitamin supplements) from two weeks prior to Visit 2 until completion of Visit 5. Paracetamol 1 g, a minimum of 4 hours between doses, up to a maximum daily dose of 4 g is permitted for occasional use, however the Investigator should be informed so that this can be recorded.
4. Volunteers should not donate blood from the enrolment visit and for 3 months following dosing.
5. Volunteers should not participate in another study whilst participating in this study.
6. Volunteers should not get out of bed for 4 hours post morning dose on Days 1, 7, 13, and 19.
7. Male volunteers should abstain from unprotected sex and sperm donation from date of consent until 4 months after last dosing.
8. Volunteers should remain resident in the [REDACTED] from the day before dosing until discharged by the [REDACTED] physician.

3.3.5 Discontinuation of subjects from treatment or assessment

3.3.5.1 Criteria for discontinuation

Volunteers may be discontinued from study treatment and assessments at any time. Specific reasons for discontinuing a volunteer from this study are:

- Voluntary discontinuation by the volunteer, who is at any time free to discontinue his/her participation in the study without prejudice to further treatment.
- Safety reasons as judged by the Investigator and/or AstraZeneca.
- Severe non-compliance to protocol as judged by the Investigator and/or AstraZeneca.

- Incorrect enrolment ie, the volunteer does not meet the required inclusion/exclusion criteria for the study.
- Volunteer lost to follow-up.

Dosing will be discontinued in the multiple dosing period (ie, during Visit 4) if the criteria below are met:

- An ALT/AST level ≥ 3 x ULN or any pattern of LFT abnormalities giving cause for concern.
- Evidence of haemolysis as evidenced by the following in two or more volunteers on active treatment.
 - Reticulocyte count of over 5%, and,

At least two of the following:

- A drop in haemoglobin below 10.5 g/dL.
- Decrease of 25% in haptoglobin. (The value post-dose to be compared with the average of two pre-dose values. The value should also be 15% below LLN).
- Increase of 25% in unconjugated bilirubin or LDH. (The value post dose to be compared with the average of two pre dose values. The value should also be 15% above ULN).
- A platelet count of below $80,000 \times 10^9/L$ confirmed by a repeat test (in the absence of obvious platelet clumping in a peripheral blood film) in two or more volunteers on active treatment.
- A QTcF >500 ms in two or more volunteers on active substance (QT interval corrected for heart rate by Fridericia method) or a QTcF prolongation >60 ms on average, sustained for more than 30 minutes, ie, present on two contiguous timepoints, in two or more volunteers on active substance based on the results of the continuous readings compared to baseline.
- Any general safety finding that in the opinion of the Investigator or SRC gives cause for concern.

Specific reasons for discontinuing a volunteer from the genetic research when genetics is a secondary objective of the study are:

- Withdrawal of consent for genetic research. A volunteer may withdraw from this genetic research at any time, independent of any decision concerning participation

in other aspects of the main study described in this protocol. Voluntary discontinuation by the volunteer will not prejudice further treatment.

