3.1.1 Stopping criteria for dose escalation

3.1.1.1 Safety Review Committee

Within each cohort dose escalation will only proceed once dosing has been completed at the previous dose level, however, it is possible that multiple dose (cohort 1) and single dose 1 (cohort 2) may run in parallel. For cohort 1, following completion of the first single dose level, the Investigator will review available safety data (blinded) to confirm that it is safe to proceed with the next single dose level. After the second single dose, a blinded Safety Review Committee (SRC) will meet to review the available safety data from single doses 1 and 2 to determine whether it is safe to proceed with the multiple dose in these individuals and the single dose 1 for cohort 2. The SRC will also review the PK data (up to 24 hours post dose as a minimum) from the single dose 1, and emerging data from the AstraZeneca Global SAD/MAD Study to confirm dose selection. Following the completion of the multiple dose, the SRC will review the available safety data from the multiple dose and the PK data (up to 24 hours post dose as a minimum) from the first two single doses.

For cohort 2 after completion of the first single dose level the SRC will meet to review safety data from the single dose 1 (cohort 2) and the PK data (up to 24 hours post dose) from the single doses in cohort 1 as a minimum. The SRC will then determine whether it is safe to proceed to single dose 2 (cohort 2) and use available PK data, and emerging data from the AstraZeneca Global SAD/MAD Study to confirm the dose. After single dose 2 (cohort 2) a SRC will meet to review the available safety data from single doses 1 and 2 (cohort 2) to determine whether it is safe to proceed to multiple dose (cohort 2) and use the PK data available from single dose 1 (cohort 2) and cohort 1 (both single and multiple doses), and emerging data from the AstraZeneca Global SAD/MAD Study to confirm the dose. The SRC will also meet following the completion of the multiple dose (cohort 2) to review safety data, and PK data if available, for internal information.

Note: All safety and PK data from the current study will be reviewed blinded.

The SRC will be chaired by an AstraZeneca Physician and will comprise the following individuals, as a minimum:

- AstraZeneca study team physician, or nominated deputy.
- AstraZeneca drug safety physician, or nominated deputy.
- AstraZeneca study team pharmacokineticist, or nominated deputy.

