3.1.1.3 Stopping criteria for dose escalation during the multiple dose phase

Escalation to the next dose level will not occur if any of the following criteria are met with the previous dose levels:

- Two or more volunteers on active treatment are discontinued because of either an ALT/AST level $\geq 3 \times ULN$ or any pattern of LFT abnormalities giving cause for concern.
- Evidence of haemolysis as evidenced by the following in two or more volunteers on active treatment.
 - Reticulocyte count of over 5%, and,

At least two of the following:

- A drop in haemoglobin below 10.5 g/dL.
 - Decrease of 25% in haptoglobin. (The value post-dose to be compared with the average of two pre-dose values. The value should also be 15% below LLN).
 - Increase of 25% in unconjugated bilirubin or LDH. (The value post-dose to be compared with the average of two pre-dose values. The value should also be 15% above ULN).
- A platelet count of below $80,000 \times 10^9/L$ confirmed by a repeat test (in the absence of obvious platelet clumping in a peripheral blood film) in two or more volunteers on active treatment.
 - A QTcF >500 ms in two or more volunteers on active substance (QT interval corrected for heart rate by Fridericia method) or a QTcF prolongation >60 ms on average, sustained for more than 30 minutes, ie, present on two contiguous timepoints, in two or more volunteers on active substance based on the results of the continuous readings compared to baseline.
 - Any general safety finding that in the opinion of the Investigator gives cause for concern.
 - Data indicate that at the next proposed dose the geometric mean steady state exposure ($C_{\max,ss}$ or $AUC_{(0-24),ss}$) will exceed 18 $\mu M.h$ and 2.5 μM , respectively.

Dosing in an individual volunteer may be discontinued in the multiple dose phase of the study (see Section 3.3.5.1 for criteria).

The stopping criteria refer to all volunteers at a specific dose level. In the event of the need to unblind the data for a given volunteer, or a given cohort, the study design will revert to a single blind study for that volunteer or cohort.

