3.4.4.2 Methods for unblinding the study

Individual treatment codes, indicating the treatment randomisation for each randomised volunteer, will be available to the Investigator at the study centre and the personnel who are independent of the study evaluation at the Drug Safety Department, AstraZeneca [REDACTED].

The individual treatment codes must not be broken except in medical emergencies when the appropriate management of the volunteer necessitates knowledge of the treatment randomisation. The Investigator must document and report to AstraZeneca any breaking of the treatment code. AstraZeneca retains the right to break the code for SAEs suspected to be causally related to an investigational product and that potentially require expedited reporting to regulatory authorities.

Treatment codes will not be broken for the planned analyses of data until all decisions on the evaluability of the data from each individual volunteer have been made and documented.

The following personnel will have access to the randomisation list:

- The personnel carrying out packaging and labelling of investigational product.
- The personnel dispensing the investigational product at the [REDACTED]
- The personnel analysing the PK samples.

The information in the randomisation list must be kept in a secure location until the end of the study.

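### Three of the four numeric criteria for stopping dosing in an individual volunteer carry a group count, so one affected volunteer can never meet them

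*Protocol*

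**What the plan says.** Protocol Section 3.1.1.3 lists the criteria that block escalation in the multiple dose phase and then turns to the single volunteer: "Dosing in an individual volunteer may be discontinued in the multiple dose phase of the study (see Section 3.3.5.1 for criteria"). Section 3.3.5.1 introduces its list in mandatory terms: "Dosing will be discontinued in the multiple dosing period (ie, during Visit 4) if the criteria below are met".

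The items in that list are:

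- Liver: an ALT/AST limit, "or any pattern of LFT abnormalities giving cause for concern". No number of volunteers is attached.
- Haemolysis: "Evidence of haemolysis as evidenced by the following in two or more volunteers on active treatment".
- Platelets: a limit confirmed by a repeat test, ending "peripheral blood film) in two or more volunteers on active treatment".
- QTcF: "A QTcF >500 ms in two or more volunteers on active substance", and the alternative limb on sustained prolongation has the same count.
- A closing item on any general safety finding that concerns the Investigator or the SRC. No count.

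On blinding, Section 3.1.1.1 states: "Note: All safety and PK data from the current study will be reviewed blinded". Section 3.1.1.3 nevertheless foresees that a volunteer or a cohort may have to be unblinded, with the design then becoming single blind for them. Section 3.4.4.2 states: "The individual treatment codes must not be broken except in medical emergencies". It adds only the sponsor's right to break the code for suspected related SAEs that may need expedited reporting.

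**The concern.** A discontinuation criterion for an individual should be one that an individual can satisfy. Here the haemolysis, platelet and QTcF items depend on whether a second volunteer has the same finding and on whether both received AZD9668. A lone case falls outside the mandatory rule however clear the finding is.

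At stake is the objectivity of the rule. Limits are fixed in advance so that stopping does not rest on judgement alone. Section 3.2.2 names haematological changes and QT prolongation among the main preclinical findings that could matter in humans. These are the areas in which the individual trigger does not operate.

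There is a second, smaller problem. Whoever applies the count must know who is on active drug, and the protocol does not say consistently how that is established while review stays blinded.

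**Working it through.** The protocol gives no operating figure for these rules, so there is nothing to reproduce. The main check is a comparison of the two lists.

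| Criterion | Group rule, 3.1.1.3 | Individual rule, 3.3.5.1 |
|---|---|---|
| ALT/AST/LFT | at least two active volunteers discontinued for it | no count |
| Haemolysis | at least two active | at least two active |
| Platelets | at least two active | at least two active |
| QTcF, both limbs | at least two active | at least two active |
| General safety finding | no count | no count |

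**Step 1: which level the list serves.** The cross-reference in 3.1.1.3 makes 3.3.5.1 the individual rule. The liver rows confirm it. The group liver rule counts volunteers who have already been discontinued, so it presupposes a separate individual trigger. That trigger exists for liver and is absent for the other three. Section 3.3.5.1 also does not say whose dosing stops once a count reaches two.

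**Step 2: what one case does.** With one affected volunteer the number of affected active volunteers is at most 1, and 1 < 2. The haemolysis, platelet and QTcF items are therefore never met by a lone case. That is 3 of the 4 numeric criteria.

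**Step 3: what blinded staff can know.** Section 3.4.3 allocates 6:2 in each ethnic cohort, which gives 12:4 when the parallel Japanese and Caucasian cohorts at a dose level are taken together. If k volunteers meet a limit and treatment has no effect on it (an assumption),

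P(at least 2 active) = Σ C(A,x)·C(P,k−x) / C(A+P,k), summed over x ≥ 2, with A active and P placebo.

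- k = 2: C(6,2)/C(8,2) = 15/28 = 0.536; C(12,2)/C(16,2) = 66/120 = 0.550.
- k = 3: 0.893 (6:2) and 0.864 (12:4).
- Without codes the count is certain only when k reaches P + 2, which is 4 of 8 or 6 of 16.

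**Step 4: illustration only.** The documents give no event risk, so p below is assumed. Among cases with at least one affected active volunteer, the share with exactly one is n·p·(1−p)^(n−1) / [1 − (1−p)^n].

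| p | n = 6 active | n = 12 active |
|---|---|---|
| 0.02 | 0.950 | 0.893 |
| 0.05 | 0.876 | 0.742 |
| 0.10 | 0.756 | 0.525 |
| 0.20 | 0.533 | 0.221 |

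For uncommon findings a lone case is the usual presentation. The table says how often the numeric item would be silent. It does not say how often dosing would continue.

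**The case against.** A reader might infer that a single volunteer who meets a limit must go on being dosed. The protocol does not support that. Section 3.3.5.1 allows discontinuation at any time for safety reasons as judged by the Investigator or the sponsor, and its mandatory list ends with an uncounted item on any finding of concern to the Investigator or the SRC. Section 3.1.1.1 lets the Principal Investigator withdraw anyone at any time. What is lost is the automatic trigger, not the ability to stop. This part of the objection stands, but it does not cure the defect: a limit stated as mandatory becomes discretionary for the single case.

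A reader might also infer that the count cannot be made at all. That is too strong as well, because 3.1.1.3 foresees unblinding and states the consequence. What remains is that 3.4.4.2 does not list checking a stopping criterion among the reasons for breaking a code.

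Nor is the difference between a permissive verb in 3.1.1.3 and a mandatory one in 3.3.5.1 a contradiction. The first says that individual discontinuation is possible and points to the criteria; the second says what follows when they are met.

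Finally, Table 1 schedules safety bloods before dosing in each dosing period, and Table 6 allows five haematology samples. Routine blood results may therefore seldom bring the haemolysis or platelet items into play between the first Visit 4 dose and follow-up. That is fair, and it is a further reason not to read the illustrative shares as a measure of harm. It does not make the wording consistent.

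**Conclusion.** The point holds as a defect of wording in a safety rule. By the protocol's own cross-reference 3.3.5.1 governs the individual volunteer, yet three of its four numeric criteria cannot be met by one individual. For those three, stopping a lone case rests on the judgement of the Investigator, the SRC or the sponsor. This follows from the text alone and needs no assumed event rate.

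The secondary point is an inconsistency about treatment codes. With two affected volunteers, blinded staff have about a 54% to 55% chance that the count is met, assuming no treatment effect. The sections on blinded review, stopping and code-breaking do not together say how the question is settled.

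**What to change.** The sponsor should reconcile Sections 3.1.1.3 and 3.3.5.1 so that each criterion is stated at the level, individual or group, at which it is meant to apply. Where a count is kept, the text should say whose dosing stops when it is reached. The clinical team decides the rule and the limits; none is proposed here.

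Sections 3.1.1.1, 3.1.1.3 and 3.4.4.2 should be aligned on who may establish that an affected volunteer is on active treatment, and how. One possibility is to use the Drug Safety personnel whom 3.4.4.2 already names as independent of the study evaluation and as having access to the individual codes. They would return only met or not met. Because the SRC includes a drug safety physician, the text should make clear that the check is made by someone else. Section 3.4.4.2 would then list this check as a permitted use of the codes.

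The cost is wording in these sections. Visits, samples and sample size do not change.
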